10.1 Extent of Exposure

The duration of exposure (days) and number of doses taken will be summarized by treatment for the Safety population using summary statistics for continuous data as well as the number and percentage of participants with:

- ≥ 7 days exposure
- 14 days exposure (completed treatment)

Treatment start and stop dates, exposure duration (days) and number of doses administered will be listed by participant.

10.2 Adverse Events

Due to the nature of the participant participation and disease, only serious AEs (SAEs), AEs of severe (Common Terminology Criteria for Adverse Events (CTCAE) Grade 3) and potentially life-threatening (CTCAE Grade 4) intensity, and AEs relating to nausea, vomiting, diarrhea, bloating and abdominal pain of any grade will be documented in the CRF. Other AEs of mild (CTCAE Grade 1) or moderate (CTCAE Grade 2) intensity are to be documented in the medical notes.

Only treatment emergent AEs and SAEs reported in the CRF will be included in the summaries, pre-treatment AEs and SAEs reported in the CRF will be included in the listings of all AEs.

All AEs will be coded using version 23.0 of MedDRA.

Treatment-emergent AEs will be summarized by treatment, system organ class (SOC) and preferred term. Summary tables will contain the number and percentage of participants and the number of events. A participant who has multiple events in the same SOC or the same preferred term will be counted only once in the participant counts but all events will be counted in the event counts. Adverse event

summaries will be sorted by the internationally agreed SOC order (Table 15) and decreasing incidence of preferred term within SOC in the EDP1815 column.

The above summary will be repeated for Treatment Phase AEs and for Follow-up Phase AEs.

AEs considered related to study treatment will also be summarized by treatment, SOC and preferred term in the same manner as described above.

All AEs, SAEs, fatal AEs, AEs leading to discontinuation of study treatment or withdrawal from the study will be listed separately by participant. Adverse events of special interest will be flagged in the listings.

10.3 Deaths, Serious Adverse Events and other Significant Adverse Events

Treatment emergent SAEs, TEAEs leading to discontinuation of study treatment or withdrawal from the study will be summarized separately by treatment, SOC and preferred term.

10.3.1 Adverse Events of Special Interest

TEAEs of nausea, vomiting, diarrhea, bloating and abdominal pain will be considered as adverse events of special interest (AESI).

AESI will be summarized by treatment, preferred term, and CTCAE grade. The summary will contain the number and percentage of participants and the number of events.

AESI will also be summarized by treatment, preferred term and relationship to study drug in the same manner.

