
To evaluate the effect of EDP1815 on length of hospitalization and recovery in participants with COVID-19	
Time to discharge, defined as the time in days from start of treatment to first occurrence of a WHO OSCI score of 2 or less.Time to oxygen saturation (SpO_2) $\geq 94\%$ on room air without further requirement for oxygen therapy.Time to recovery, defined as the time in days from symptom onset to alleviation of all COVID-19 symptoms.

To evaluate the safety and tolerability of EDP1815 in participants with COVID-19	
Incidence and severity of treatment emergent adverse events and serious adverse events.Incidence of clinically significant abnormal changes in safety laboratory parameters.
Exploratory	

To evaluate the effect of EDP1815 on the exaggerated host cytokine response to COVID-19 infection	
Change from baseline in cytokine levels (including IL-6) at day 4 and day 7 (and/or at additional timepoints if samples are available).Change from baseline in inflammatory response at day 4 and day 7 (and/or at additional timepoints if samples are available).

To identify clinical or biochemical predictors of response to EDP1815, and to confirm lack of systemic absorption.	
Statistical significance of each potential predictor-treatment interaction in exploratory models based on the final selected model for the primary efficacy analysis.To identify the presence of EDP1815 in stool and/or blood using PCR primers

4. Study Design

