9.4.2. Safety Analyses

All safety endpoints will be tabulated by treatment group and will be performed on the Safety Population. Further details will be described in the SAP.

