Examples of such events include invasive or malignant cancers, intensive treatment in an emergency room or at home for allergic bronchospasm, blood dyscrasias or convulsions that do not result in hospitalisation, or development of drug dependency or drug abuse.

Recording and Follow-Up of AE and/or SAE

AE and SAE Recording

- Due to the nature of the patient population and disease only SAEs and CTCAE grade 3 and grade 4 AEs will be documented in the CRF. Grade 1 and 2 AEs should be documented in the medical notes. However, adverse events relating to nausea, vomiting, diarrhoea, bloating and abdominal pain of any grade will be recorded and assessed as an adverse event.
- When an AE of severe intensity / SAE occurs, it is the responsibility of the investigator to review all documentation (e.g. hospital progress notes, laboratory reports, and diagnostics reports) related to the event.
- The investigator will then record all relevant AE/SAE information in the CRF.
- It is **not** acceptable for the investigator to send photocopies of the participant's medical records to the Sponsor in lieu of completion of the AE/SAE CRF page.
- There may be instances when copies of medical records for certain cases are requested by the Sponsor. In this case, all participant identifiers, with the exception of the participant number, will be redacted on the copies of the medical records before submission to the Sponsor.
- The investigator will attempt to establish a diagnosis of the event based on signs, symptoms, and/or other clinical information. Whenever possible, the diagnosis (not the individual signs/symptoms) will be documented as the AE/SAE.

Assessment of Intensity

The severity, or intensity, of an AE refers to the extent to which an AE affects the participant's daily activities or their health. The intensity of the AE will be rated in accordance with the CTCAE version 5.0.

Changes in the severity of an AE should be documented to allow an assessment of the duration of the event at each level of intensity to be performed. Adverse events characterized as intermittent do not require documentation of onset and duration of each episode.

An event is defined as 'serious' when it meets at least 1 of the predefined outcomes as described in the definition of an SAE.

Assessment of Causality

- The investigator is obligated to assess the relationship between study intervention and each occurrence of each AE/SAE.

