7.3.3 Adverse Event Information

AEs with missing severity will be considered as 'Severe' for summary purposes but recorded as missing in the listings.

AEs with missing relationship will be considered 'Related' for summary purposes but recorded as missing in the listings.

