7.4.2 Planned Schedule of Interim Analyses

Interim analyses are planned after 10, 20, 30, 40 and 60 participants have completed 7 days follow-up after their last dose (Day 21 for participants who complete dosing as scheduled).

At all interim analyses, the DMC will review safety and study disposition data to assess the safety of the interventions and to monitor the overall conduct of the study. Safety review will focus on the number and details of severe and serious adverse events, gastrointestinal (GI) events of any grade and laboratory data which meets the criteria for potentially clinically important (PCI).

At the second interim, after 20 participants have completed 7 days of follow-up after their last dose, the DMC will also specifically address the question of recruitment can be opened to participants aged >65 years.

At the final interim, after 60 participants have completed 7 days of follow-up after their last dose, the DMC will also review the efficacy data in order to make a recommendation on whether recruitment should be extended to a further 40 participants.

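### Severity of treatment-emergent adverse events is tabulated only for five GI terms, although it is part of a secondary endpoint and a named DMC review item

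*SAP*

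**What the plan says.** The protocol's objectives table (Section 3, Table 2, repeated in the synopsis) sets the first safety endpoint as "Incidence and severity of treatment emergent adverse events and serious adverse events". Protocol 9.4.2 adds: "All safety endpoints will be tabulated by treatment group and will be performed on the Safety Population". Protocol Appendix 3 supplies the scale: "The intensity of the AE will be rated in accordance with the CTCAE version 5.0".

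SAP 10.2 limits the main summary to two dimensions: "Treatment-emergent AEs will be summarized by treatment, system organ class (SOC) and preferred term". Related, serious and discontinuation or withdrawal TEAEs follow the same layout (SAP 10.2 and 10.3). Grade appears once, for the five GI symptoms in SAP 10.3.1: "AESI will be summarized by treatment, preferred term, and CTCAE grade".

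Three other provisions matter:
- SAP 10.2 and Protocol 8.3 restrict the CRF to serious events, Grade 3 and Grade 4 events, and the five GI symptoms at any grade.
- SAP 7.3.3 has a rule for gaps in severity: "AEs with missing severity will be considered as 'Severe' for summary purposes". In listings the value stays missing.
- SAP 7.4.2 describes the DMC's task: "Safety review will focus on the number and details of severe and serious adverse events, gastrointestinal (GI) events of any grade". Laboratory values meeting the SAP's criteria for potential clinical importance complete that list.

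**The concern.** An endpoint with two components, incidence and severity, has a table plan that addresses mainly the first. If the output list is followed as written, a reader of the study report cannot look up how many participants in each arm had a severe event. The DMC is asked to look at the number of severe events and receives a table of serious ones, but none of severe ones. Seriousness is not a substitute: Protocol Appendix 3 defines it by outcome and rates intensity separately by CTCAE.

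The distinction between Grade 3 and Grade 4 also matters within the protocol itself. Sections 7.2.1 and 7.2.2 attach different dosing consequences to the two grades, yet outside the GI terms no table shows them apart.

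**Working it through.** The plan states no figure to reproduce, so the check is a count of planned outputs and an account of what can be recovered from them.

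**Step 1: count the adverse event tables in SAP 16.3.1.**

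| Table(s) | Content | Grade shown? | DMC flag |
|---|---|---|---|
| 14.3.1.1.1 to 14.3.1.1.3 | All, treatment-phase and follow-up TEAEs | No | Unblinded |
| 14.3.1.1.4 | All TEAEs by age group | No | Safety (only if over-65s are admitted) |
| 14.3.1.2 | Related TEAEs | No | None |
| 14.3.2.1 | Serious TEAEs | No | Unblinded |
| 14.3.2.2, 14.3.2.3 | TEAEs leading to discontinuation or withdrawal | No | None |
| 14.3.2.4 | Fatal TEAEs | No | None |
| 14.3.2.5.1 | Five GI terms by grade | Yes | Unblinded |
| 14.3.2.5.2 | Five GI terms by relationship | No | Unblinded |

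Total: 3 + 1 + 1 + 1 + 2 + 1 + 1 + 1 = 11. With grade: 1. Covering all TEAEs by grade: 0. Limited to Grade 3 or higher: 0. The five adverse event listings (16.2.7.1 to 16.2.7.5) all go unblinded to every DMC meeting.

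**Step 2: what the CRF rule allows one to infer.** Take any SOC or preferred-term row that excludes the five GI terms. If sites follow the recording rule, each event in it is Grade 3, Grade 4 or serious. Let P_all be the participants in that row of the all-TEAE table and P_ser those in the same row of the serious table. Anyone counted in the first but not the second had a non-serious event, which must be Grade 3 or 4. So, within one row,

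P_all − P_ser ≤ participants with a Grade 3 or higher event ≤ P_all.

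The interval has width P_ser, because serious events enter the CRF at any grade and their grade is not tabulated.

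**Step 3: why the rows do not add up to an arm total.** SAP 10.2 counts a participant once per SOC and once per preferred term. A participant with events in two SOCs is in both. If a and b participants have a severe event in two SOCs, the number with either lies anywhere from max(a, b) to a + b. An overall any-TEAE row, if the shells have one, would not resolve this, since it also includes participants whose only event is a Grade 1 or 2 GI symptom.

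**Step 4: what no table gives.**
- Participants per arm with any Grade 3 or higher TEAE (Steps 2 and 3 give bounds only).
- Grade 3 versus Grade 4 outside the five GI terms.
- Serious events below Grade 3 outside those terms, as distinct from serious events at Grade 3 or higher.

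**Step 5: the listings.** These presumably show grade, since SAP 7.3.3 says how missing severity appears there, but the listing columns are not given. A hand count from them would also depart from the SAP's own convention, because an event with missing severity is severe in a summary and blank in a listing.

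**Step 6: likely origin.** SAP 4.1 lists the safety objective, but SAP Table 1 has no endpoint row for it, and SAP Section 14 declares no changes to the protocol. An oversight fits this better than a deliberate choice, though the documents do not say.

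**The case against.** The best reply is that the CRF rule already does most of the work. Outside the five GI terms nearly every row is a count of severe or serious events, and those five terms are exactly the ones tabulated by grade. Serious and fatal TEAEs have their own tables. The DMC receives the all-TEAE, serious and GI-by-grade tables plus five unblinded listings at every meeting, and Protocol 6.6.1 lets it ask for unblinded data. SAP 7.4.2 names several review items, of which severe events are one, and it asks for details as well as numbers. The missing-severity rule is usable in Table 14.3.2.5.1. Finally, this is a descriptive pilot of 60 participants, extendable to 100.

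Much of this stands. A reader might infer that severity goes unreported or that the DMC cannot see it; the tables and listings just described rule that out. A reader might also infer that mild GI events will dominate the totals and hide an imbalance elsewhere. The documents give no such ranking: Protocol 2.4 mentions headache and diarrhoea as mild events, Protocol 2.2 expects no adverse drug reactions, and GI symptoms have their own rows.

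What does not stand is that nothing is missing. The three items in Step 4 remain unavailable from any table, and Protocol 9.4.2 promises tabulation, which a listing does not provide.

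**Conclusion.** The gap is real and limited. TEAE severity, half of a stated secondary endpoint and part of the DMC's stated focus, is tabulated in 1 of 11 adverse event tables, for five GI terms. Elsewhere it is recoverable only in part, through the CRF rule, the serious and fatal tables, and the listings.

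The conclusion rests on the output list in SAP Appendix 1 being complete. The partial recovery in Step 2 assumes that sites apply the CRF rule consistently and that events of the five GI terms can be separated cleanly by preferred term. No sample size, interval width or error rate is affected. The SAP should be corrected before database lock, and preferably before the next DMC meeting; the trial's design does not depend on it.

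**What to change.** Add one table to SAP 10.2 and Appendix 16.3.1: TEAEs by treatment, SOC, preferred term and maximum CTCAE grade.
- Count each participant once, at the worst grade, within each level and overall.
- Include an overall row for any TEAE of Grade 3 or higher and another for Grade 4 or higher.
- To identify serious events below Grade 3, show serious events by grade in the same table or add grade to Table 14.3.2.1.
- Flag the table DMC-Unblinded.
- State in SAP 7.3.3 which CTCAE grade the imputed value of severe corresponds to. SAP 10.2 labels Grade 3 as severe, but 7.3.3 does not make the link.

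The cost is one more table shell and program. Intensity is already rated by CTCAE under Protocol Appendix 3, so no new data are needed.

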10.4 Clinical Laboratory Evaluations

Local laboratory data will be used for all safety laboratory evaluations. Blood samples for safety laboratory evaluations will be collected at Baseline, Day 4 and Day 7. [Table 17](#) shows the parameters which will be collected and the units in which they will be supplied.

Laboratory data (hematology and chemistry parameters) will be summarized by treatment and visit. Changes from baseline at Day 4 and Day 7 will also be summarized.

Relative differentials (neutrophils, lymphocytes, monocytes, eosinophils and basophils) will be converted to absolute values as described in [Section 5.3.4.3](#).

The number and percentage of participants showing shifts from baseline to worst-case post-baseline with respect to the normal ranges will also be summarized for each parameter. Categories will be:

- Low
- Normal
- High

The determination of worst-case post-baseline will consider both scheduled (Day 4 and Day 7) and any unscheduled assessments which occur after the first dose of study treatment. Percentages will use the number of participants with at least one post-baseline assessment available. If the baseline value is missing it will be assumed to be normal for this summary. Worst-case can be either High or Low and if a participant has post-Baseline values both above and below the normal range then they will be counted in both relevant categories.

Safety laboratory values are also flagged for potentially clinically important (PCI) values if they meet any of the criteria for Grade 2 or higher events according to CTCAE V5.0 with the exception of lymphocytes where the lower limit for grade 3 is used as COVID-19 cases lymphopenia in most patients. The PCI criteria are listed in [Table 17](#). The number and percentage of participants showing shifts from baseline to worst-case post-baseline with respect to PCI criteria will be summarized for all parameters where PCI criteria have been defined. Categories will be:

- Low
- Within range
- High

The determination of worst-case post-baseline will consider both scheduled (Day 4 and Day 7) and any unscheduled assessments which occur after the first dose of study treatment. Percentages will use the number of participants with at least one post-baseline assessment available. If the baseline value is missing it will be assumed to be within range for this summary. Worst-case can be either High or Low and if a participant has post-Baseline values both above and below the PCI criteria then they will be counted in both relevant categories.

Safety laboratory data will be listed by participant, including changes from baseline, normal ranges and flags for measurements outside the normal range and flags for meeting PCI criteria. In addition, for participants who meet at least one PCI criteria, all values within the laboratory type (hematology or clinical chemistry) will be listed separately.

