1.3. Schedule of Activities (SoA)

Figure 2: Schedule of Activities

Data	Screening [^] (Day -1 to Day 0)	Baseline [^] (Day -1 to Day 0)	D 1 [^]	D 2	D 3	D 4	D 5	D 6	D 7	D 8	D 9	D 10	D 11	D 12	D 13	D14 or day of discharge ^{&}	D21 ~ (Follow-up Telephone Visit)	D42 (Final Follow-Up Telephone Visit)
Informed consent	x																	
Inclusion and exclusion criteria	x																	
Demographics and anthropomorphic data (e.g. age, height, weight)	x																	
Smoking status ⁹	x																	
Medical history	x																	
Significant Covid-19 Comorbidities	x																	
Physical examination	x																	
Pregnancy test (blood/urine) ¹	x																	
Vital signs ^{#*}		x	x	x	x	x	x	x	x	x	x	x	x	x	x	x		
Concomitant Medications [#]	x	x	x	x	x	x	x	x	x	x	x	x	x	x	x	x	x	
Oxygen therapy status [#]		x	x	x	x	x	x	x	x	x	x	x	x	x	x	x	x	
SaO ₂ /FiO ₂ status ^{#2*}		x	x	x	x	x	x	x	x	x	x	x	x	x	x			
Blood tests (FBC, CRP, LFT, Creatinine, Urea and Electrolytes, Ferritin, D-		x				x ³			x ³									

Data	Screening [^] (Day -1 to Day 0)	Baseline [^] (Day -1 to Day 0)	D 1 [^]	D 2	D 3	D 4	D 5	D 6	D 7	D 8	D 9	D 10	D 11	D 12	D 13	D14 or day of discharge ^{&}	D21 ~ (Follow-up Telephone Visit)	D42 (Final Follow-Up Telephone Visit)
dimer, Troponin) ^{#*}																		
HIV test	x																	
Cytokine Panel, Paxgene sample, and Biobanking sample*		x				x ³			x ³									
Plasma PCR for EDP1815									x ³									
Day since onset of symptoms [#]		x																
8-point ordinal scale [#]		x	x	x	x	x	x	x	x	x	x	x	x	x	x	x	x	x
COVID-19 RTPCR [#]	x																	
Review of adverse events ^{#*@}	x	x	x	x	x	x	x	x	x	x	x	x	x	x	x	x	x	x
Retrieval of relevant clinical data ⁴																		x
Outpatient questionnaire ⁵			x	x	x	x	x	x	x	x	x	x	x	x	x ⁶	x ⁶	x ⁶	
Telephone call ⁵								x							x	x	x	
Discharge status [#]			x	x	x	x	x	x	x	x	x	x	x	x	x	x	x	
Mortality status [#]			x	x	x	x	x	x	x	x	x	x	x	x	x	x	x	
Faecal sample for microbiome analysis		x ⁷							x ⁷									
EDP1815 or Placebo administration ⁸			x ⁸	x ⁸	x ⁸	x	x	x	x	x	x	x	x	x	x			

[^] Due to the urgent nature of the study, screening, baseline and Day 1 assessments can occur on the same day. Eligible patients will be randomized and dosed as soon as possible after eligibility is confirmed.

[~] This assessment can be performed between days 20-22.

#Results will be extracted from the patient record where available – no research specific test may be required.

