CDISC standards will not be used for this study. The analysis datasets will be produced using a similar structure to those described for the analysis dataset model (ADaM) but will be not be fully validated and will be programmed directly from the source CRF and external data rather than from SDTM datasets.

All analyses will be performed using SAS version 9.2 or higher (SAS Institute, Cary, NC, USA).

14 Summary of Changes to the Protocol

Not applicable.

15 References

Fine, J. a. (1999). A Proportional Hazards Model for the Subdistribution of a Competing Risk. *Journal of American Statistics Association*, 94(446), 496-509.

16 Appendix 1: List of Tables, Figures and Listings

All outputs detailed in the following sections will be produced for the final analysis. Programming notes also indicate where tables will be produced for interims using the following abbreviations:

DMC-Blinded – produced as a blinded output with only the overall column shown - all DMC meetings

DMC-Unblinded – produced as an unblinded output – all DMC meetings

DMC-Safety – produced as an unblinded output – all DMC meetings after participants aged >65 years have been approved for inclusion

DMC-Efficacy – produced as an unblinded output – DMC meeting after 60 participants have completed 21 days treatment only

Note that some outputs will only be produced if the criterion specified in the programming notes is met.

Highlighted **XXXXX** text indicates that the full title is dependent on currently unknown factors (e.g. name of medications which becomes SOC during the study).

If the study is stopped early, outputs will be produced as specified in Early Stop column.

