16.3 Safety

16.3.1 Tables

Number	Title	Population	Early Stop	Programming notes ¹
14.3.1.1.1	Summary of All TEAEs by System Organ Class and Preferred Term	Safety	Yes	DMC-Unblinded
14.3.1.1.2	Summary of Treatment Phase TEAEs by System Organ Class and Preferred Term	Safety	Yes	DMC-Unblinded
14.3.1.1.3	Summary of Follow-up Phase TEAEs by System Organ Class and Preferred Term	Safety	Yes	DMC-Unblinded
14.3.1.1.4	Summary of All TEAEs by Age Group, System Organ Class and Preferred Term	Safety		DMC-Safety Only produced if participants aged >65 are permitted to enter the study
14.3.1.2	Summary of Treatment-Related TEAEs by System Organ Class and Preferred Term	Safety	Yes	
14.3.2.1	Summary of Serious TEAEs by System Organ Class and Preferred Term	Safety	Yes	DMC-Unblinded
14.3.2.2	Summary of TEAEs Leading to Permanent Discontinuation from Study Drug by System Organ Class and Preferred Term	Safety	Yes	
14.3.2.3	Summary of TEAEs Leading to Withdrawal from the Study by System Organ Class and Preferred Term	Safety	Yes	
14.3.2.4	Summary of Fatal TEAEs by System Organ Class and Preferred Term	Safety	Yes	

Number	Title	Population	Early Stop	Programming notes ¹
14.3.2.5.1	Summary of TEAEs of Special Interest by Preferred Term and CTCAE Grade	Safety	Yes	DMC-Unblinded
14.3.2.5.2	Summary of TEAEs of Special Interest by Preferred Term and Relationship to Study Drug	Safety	Yes	DMC-Unblinded
14.3.4.1.1	Summary of Change from Baseline in Hematology	Safety	Yes	
14.3.4.1.2	Summary of Shifts from Baseline to Worst-case Post-Baseline with Respect to the Normal Range in Hematology	Safety	Yes	DMC-Unblinded
14.3.4.1.3	Summary of Shifts from Baseline to Worst-case Post-Baseline with Respect to the PCI Criteria in Hematology	Safety	Yes	DMC-Unblinded
14.3.4.1.4	Summary of Shifts from Baseline to Worst-case Post-Baseline with Respect to the PCI Criteria in Hematology, by Age Group	Safety		DMC-Safety Only produced if participants aged >65 are permitted to enter the study
14.3.4.2.1	Summary of Change from Baseline in Clinical Chemistry	Safety	Yes	
14.3.4.2.2	Summary of Shifts from Baseline to Worst-case Post-Baseline with Respect to the Normal Range in Clinical Chemistry	Safety	Yes	DMC-Unblinded
14.3.4.2.3	Summary of Shifts from Baseline to Worst-case Post-Baseline with Respect to the PCI Criteria in Clinical Chemistry	Safety	Yes	DMC-Unblinded

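### Laboratory shift tables enter a missing baseline as normal; for lymphocytes in the normal-range table the SAP's own remark on lymphopenia makes that unlikely, and a separate 'Missing' row would be better (minor)

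*SAP*

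**What the plan says.** SAP 10.4 defines two kinds of laboratory shift table, from baseline to worst post-baseline value.

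- **Normal-range tables** (categories Low, Normal, High): "If the baseline value is missing it will be assumed to be normal for this summary".
- **PCI tables** (categories Low, Within range, High): "If the baseline value is missing it will be assumed to be within range for this summary".

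SAP 10.5.1 repeats the within-range rule for vital signs. None of these tables has a category for a missing baseline. The denominator does not require one either: "Percentages will use the number of participants with at least one post-baseline assessment available".

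SAP 10.4 sets the PCI flags at CTCAE grade 2 or higher, "with the exception of lymphocytes where the lower limit for grade 3 is used as COVID-19 cases lymphopenia in most patients" ('cases' evidently stands for 'causes'). The section makes no matching allowance in the missing-baseline rule.

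In the Protocol's Schedule of Activities (1.3), the blood-test row carries a footnote: "Results will be extracted from the patient record where available". So a missing baseline can occur.

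SAP 16.3.1 lists Table 14.3.4.1.2, "Summary of Shifts from Baseline to Worst-case Post-Baseline with Respect to the Normal Range in Hematology", and its PCI and chemistry counterparts (14.3.4.1.3, 14.3.4.2.2, 14.3.4.2.3) with the unblinded DMC flag. SAP Appendix 1 defines that flag: "DMC-Unblinded – produced as an unblinded output – all DMC meetings".

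**The concern.** A participant with no pre-dose lymphocyte count and a low count on Day 4 appears in the table as having gone from normal to low after dosing. On the SAP's own statement, low was the more likely state before dosing. The table would show an observed normal baseline and an assumed one in the same cell, and no version without the assumption is planned.

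The DMC reads these tables unblinded. One of its meetings, after 20 participants, informs the decision on recruiting people over 65 (SAP 7.4.2). With arms this small, a few assumed baselines can change how a table reads.

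**Working it through.** The plan gives no figure on this point, so there is nothing of its own to reproduce. The check has two parts: where the assumption conflicts with the SAP, and how large the effect could be.

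**1. Where the conflict lies**

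| Table | Does the lymphopenia statement bear on it? |
|---|---|
| 14.3.4.1.2, hematology, normal range | Yes. Any low lymphocyte count is in play. |
| 14.3.4.1.3, hematology, PCI | Weakly. The lymphocyte limit is already grade 3 (below 0.5 × 10³/µL, SAP Table 17), so mild lymphopenia is not flagged. |
| 14.3.4.2.2 and 14.3.4.2.3, chemistry | No. They contain no lymphocytes, and the documents offer no comparable statement for their parameters. |
| 14.3.5.2, vital signs, PCI | No. |

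**2. Expected number of false shifts in 14.3.4.1.2**

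Expected false normal-to-low shifts per arm = n × m × q × r, where

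- n = 30 per arm (60 randomized 1:1, Protocol 9.1), all taken to have a post-baseline value;
- m = share with no baseline value: not in the documents, assumed 5% or 10%, with 20% as a stress case;
- q = share lymphopenic at baseline: the SAP says only 'most', assumed 51% to 80%;
- r = share of those still low after baseline: assumed 1, with 0.8 as a variant.

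Missingness is taken as unrelated to arm and to the lymphocyte count.

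| m | q = 51% | q = 80% |
|---|---|---|
| 5% | 30 × 0.05 × 0.51 = 0.8 | 30 × 0.05 × 0.80 = 1.2 |
| 10% | 30 × 0.10 × 0.51 = 1.5 | 30 × 0.10 × 0.80 = 2.4 |
| 20% | 30 × 0.20 × 0.51 = 3.1 | 30 × 0.20 × 0.80 = 4.8 |

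With r = 0.8, the range for 5% to 10% missing falls to 0.6 to 1.9.

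**3. Share of reported shifts that would be false**

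Suppose, as a further assumption, that 20% of truly normal participants become low. With r = 1, the false share is mq / (mq + 0.2(1 − q)).

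- m = 5%: 0.0255 / (0.0255 + 0.098) = 21% at q = 51%; 0.04 / (0.04 + 0.04) = 50% at q = 80%.
- m = 10%: 0.051 / (0.051 + 0.098) = 34% at q = 51%; 0.08 / (0.08 + 0.04) = 67% at q = 80%.

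**4. Difference between arms**

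The expected count is the same in both arms, so the expected difference is zero. Chance differences remain. Taking the false shifts in each arm as independent Binomial(30, mq), the probability that the arms differ by 3 or more is about 4% to 9% at 5% missing, 13% to 23% at 10%, and 28% to 38% at 20%.

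**5. After the change**

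With a separate 'Missing' baseline row, false shifts from normal due to missing baselines are zero by construction. The same participants still appear, in their own row.

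**The case against.** The strongest defence is that the rule is deliberate. The SAP resolves missing safety data towards over-reporting elsewhere too: missing severity becomes severe and missing relationship becomes related (7.3.3), and events with missing dates count as treatment-emergent unless there is clear evidence otherwise (5.3.4.2). Assuming a normal baseline means that no later abnormality is excused for lack of a baseline. The rule applies equally to both arms. This stands, and it rules out a claim of systematic bias.

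Missing baselines should also be uncommon:

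- Baseline is the last non-missing pre-dose value, and untimed Day 1 data count as pre-dose (SAP 5.3.1.2).
- Routine tests done before consent may be used if they fall within the scheduled window (Protocol 8).
- The differential white cell count is to be measured in all participants at baseline (Protocol 8.5.1).

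This also stands as a limit on frequency, though it does not justify the rule.

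Finally, the DMC's laboratory review focuses on PCI values (SAP 7.4.2). For anyone with a PCI value, it receives listings 16.2.8.2 and 16.2.8.4, where an absent baseline can be seen. That check works for PCI values only. The full laboratory listings, 16.2.8.1 and 16.2.8.3, are not flagged for the DMC. For a low but non-PCI lymphocyte count, nothing flagged for the DMC reliably separates an observed normal baseline from an assumed one.

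The defence does not show that the assumption is needed. A 'Missing' row reports every one of these abnormalities too, without asserting an unobserved baseline.

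**Conclusion.** The point holds as a minor reporting weakness. Participants with no baseline laboratory value are shown as normal or within range, and for lymphocytes in Table 14.3.4.1.2 this runs against the SAP's own description of the disease. On the assumed values above (30 per arm, 5% to 10% missing, 51% to 80% lymphopenic, all still low afterwards), the effect is about 0.8 to 2.4 false normal-to-low shifts per arm. If baselines are almost never missing, it is close to nothing.

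A reader might infer three stronger claims that the documents do not support.

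- **That abnormalities present at admission are in general reported as new.** This happens only to participants with no pre-dose value and an abnormal later one.
- **That the lymphopenia statement discredits all the shift tables.** It bears fully on one of them.
- **That the DMC would see a spurious drug effect.** With 10 per arm at the 20-participant meeting, 3 missing baselines in one arm and none in the other would give 3 × 0.5 = 1.5 to 3 × 0.8 = 2.4 false shifts, or 15% to 24% of that arm. The chance of 3 or more missing in one arm and none in the other, in either direction, is about 1.4% at 5% missing and 4.9% at 10%, and at most about 7% (at 15% to 20% missing). That is a possible accident, not an expected effect.

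The tables are descriptive. SAP 7.4.2 and 7.4.3 set no numerical shift-table threshold for the decision on participants over 65. No primary or inferential result is touched.

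**What to change.** In SAP 10.4, replace both missing-baseline assumptions with a separate 'Missing' baseline row in the normal-range and PCI shift tables. Show the number of such participants per arm and their worst post-baseline category within that row. Apply the same layout to the versions by age group. Make the same change in 10.5.1 for consistency only, since nothing in the documents argues specifically against the rule for vital signs.

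Keep these participants in the tables and in the safety review. Restricting the count of new abnormalities to those with an observed normal baseline would be a different step: it could drop genuine toxicities from the count, and it is not proposed here.

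The cost is one extra row per table and a few words in the SAP. No data collection, denominator or listing has to change.
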